1. Inability to speak English or Runyankole	Lack of available interpreters for effective communication in other languages; It is anticipated 100% of clinicians at this facility speaks one of these two languages

Peripartum Women

Inclusion criteria	Rationale
1. Age >18	We will exclude women under the age of 18 because even if they are considered emancipated minors, most are not adults physiologically. Our research questions are designed to study physiologic monitoring in adult women, and may not apply equally to pregnant children under the age of 18. Moreover, this the wireless device currently only has food and drug safety approval for adult use.
2. Undergoing emergency cesarean delivery at MRRH	Women undergoing emergency cesarean are chosen due to increased risk of morbidity and mortality in this population. Additionally, the study proposes to test monitoring in the first 24 hours after birth, therefore women delivered outside of MRRH and arriving in the postpartum period will arrive after this period has begun and will miss the critical window to initiate monitoring.

3. Able to provide consent or have a guardian/attendant present who can consent on their behalf.	The latter is included as monitoring critically ill women who may be unable to provide their own consent is paramount to ultimately affecting clinical outcomes
4. Willing to wear the biosensor for 24 hours	
5. Willing to remain in the postpartum unit for 24 hours	Wearing the monitor is integral to the proposed intervention. Given the technical capabilities of the monitor, current wireless signals will only be available on the postpartum ward, therefore women will need to be present on the ward for the device to transmit signals to the central monitor and alerts to clinicians should abnormalities occur.
Exclusion Criteria	Rationale
1. Admitted to ICU directly after delivery	The ICU at MRRH is a closed unit in a separate building from the postpartum ward, as such, monitoring systems in use there are different from on the postpartum ward. The aim of this study is to investigate the use of wireless monitoring for women admitted to the postpartum ward after delivery.
2. Known allergies or hypersensitivity to device materials	For this research we will be limited to using standard electrode adhesives to apply the device. To avoid adverse reactions, any women with allergies or known hypersensitivity to the device will be excluded.

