16. At the end of 24 hours of monitoring each enrolled woman who participated in monitoring will have a brief structured questionnaire on the acceptability of the monitoring, which will be administered by the research assistant. *See Appendix 4 – Postpartum Woman Acceptability Questionnaire.* This is estimated to take ~15 minutes.

17. Up to 30 enrolled women will be asked to participate in an in-depth interview on the experience of wearing the wireless monitor. This is conducted to provide context to the above quantitative measures and to understand acceptability and facilitators and barriers to uptake of wireless physiologic monitoring. Women will be purposively sampled for age (18-34 and >35 years) and level of use of the monitor (~15 women who completed 24 hours of monitoring and ~ 15 women with less than 24 hours of monitoring). Interviews will be conducted until thematic saturation is reached. *See Appendix 6 – Postpartum Woman Interview Guide.* This interview is estimated to take ~45 minutes. Interviews will occur in a private room, and prior to discharge but after wireless monitoring is complete (postpartum day 2 and 3 at a time convenient to women. A digital recorder will be used to record interviews and the trained research assistant will then transcribe and translate administered to clinician and post-partum women participants.

18. After these study procedures are complete women will be approached to complete the medical trust researcher scale (Appendix 11) and the QuiC scale (Appendix 12). Additionally, the pain assessment and state trait scale will be repeated (Appendix 10 and 11).

19. Up to 15 enrolled women (distinct from those participating in step 17 above) will be invited to participate in an in-depth interview (Appendix 13) to explore their experiences of going through the informed consent process. Up to 15 women who declined monitoring will be invited to participate in the in-depth interview only (no monitoring) (Appendix 15). A separate consent form will be used for these women (Appendix 14)

20. After every 24 hours of monitoring, data from biosensors which includes continuous physiologic sign data, start and stop time of monitoring and potential interruptions will be downloaded by the research assistant into a secure database. Data from the emergency cellular phone including number of alerts received, time received and time read will also be downloaded and extracted from the cellular phone.

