21. The research assistant will also document any external factors that may affect monitoring every 24 hours e.g. electricity outages or cellular network disruptions, and stock outs

22. After discharge, all patients who completed at least 12 hours of monitoring will receive an invitation to complete a short mobile phone survey to measure functionality, mobility, and wellness at day 1, and at 2,4,6 and 12 weeks post discharge (Appendix 16). At 6 weeks post discharge they will also receive survey assessing for health expenditure, depression and postpartum complications (Appendix 17). The questionnaire will be administered by an automated mobile phone survey system , that allows the participants to receive a prerecorded voice call with the survey and instructs them on answer choices. This will be administered through Engage Spark. EngageSPARK is a social enterprise that offers a browser-based, cloud-hosted platform used to launch interactive Voice IVR and SMS text message campaigns globally. This platform has previously been used in studies of providing airtime incentives to survey participants in Uganda as well as Bangladesh and Colombia. A research assistant will call participants to administer the survey for participants unable to access or complete automated phone surveys. Up to 5 attempts will be made to reach the participant to complete the survey. Participants will receive instruction from a RA on the automated survey at the time of their baseline/acceptability interview conducted as part of the parent study (study procedure #16)

23. At 12 weeks post discharge a research assistant will call participants to administer the last set of surveys as well as an acceptability questionnaire on the use of automated surveys to collect patient reported outcome measures (PROMS) (Appendix 17). Up to 5 attempts will be made to research participants for the survey at these time points.

Table 3: Survey administration timeline

	Day after discharge	2 weeks post discharge	4 weeks post discharge	6 weeks post discharge	12 weeks post discharge
Mobility survey	x	x	x	x	x
Financial Survey				x	x
General Survey				x	x
EPDS				x	x
Acceptability Survey				x	x

Biostatistical Analysis

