Aim 6: From the QUIC scale two scores are calculated: 1) the Informed Consent Aggregate Score (ICAS) and 2) the Therapeutic Misconception Aggregate Score (TMAS). ICAS assesses the quality of consent, ranging from 0-10 (10 is a perfect score) and TMAS assesses the presence of a therapeutic misconception (TMAS), ranging from 0-5 (5 is a perfect score). The ICAS and TMAS scores will be calculated and the means and standard deviations summarized for all participants. We will also summarize individual questions to understand the quality of specific elements of informed consent process. We will compare ICAS and TMAS between women in different stages of labor using one-way ANOVA, and with different pain scores using Spearman correlation and linear regression. Multiple

linear regression will be used to assess the independent association of covariates of interest (demographics, stage of labor, pain score, anxiety, obstetric history and trust) with ICAS and TMAS scores.

Aim 7: Using the motion metric on the wireless device we will summarize mobility in the first 24 hours after their cesarean both as a continuous variable ,and categorizing women into those with low and high mobility. We will summarize the functional status of women in the post discharge period according to the five dimensions measured by the mobility survey : (ability to move independently, ability to selfcare, ability to perform usual activities, level of energy, and overall health, as well as a composite variable with scores of 1-4. 1 being poorest functional status and 4 being better functional status) We will describe functionality at the different time points after discharge using frequency and percent. We will compare return to functionality at the different time points by mobility category in the first 24 hours using regression modelling. We will also describe the rates of impoverishing and catastrophic expenditure after surgery. Summary statistics will be calculated for all expense types. We will compare impoverishing and catastrophic expenditure rates between women with different functional status and early mobility.

Sample Size:

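### The 12-hour monitoring gate on the post-discharge surveys also restricts expenditure results that need no motion data, so those rates may be biased by an unknown amount and in an unknown direction.

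*Protocol*

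**What the plan says.** The gate is in the Protocol, Study Procedures, item 22: "After discharge, all patients who completed at least 12 hours of monitoring will receive an invitation to complete a short mobile phone survey". The same women then get the longer questionnaire: "At 6 weeks post discharge they will also receive survey assessing for health expenditure, depression and postpartum complications". Table 3 places the financial, general and depression surveys at both 6 and 12 weeks, and item 23 covers the 12-week calls. No other route is described by which a woman monitored for under 12 hours would give these data.

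Aim 7 (Protocol, Biostatistical Analysis) uses the data in several ways. The exposure comes from the device: "Using the motion metric on the wireless device we will summarize mobility in the first 24 hours after their cesarean". Functional status comes from the phone survey. For expenditure there is a plain description, "We will also describe the rates of impoverishing and catastrophic expenditure after surgery", followed by a comparison across levels of functional status and of early mobility. Nothing there limits the results to women with at least 12 hours, compares them with women below 12 hours, or adds a sensitivity analysis. The SAP (Study Objectives and Summary) lists Aims 1 to 3 only, so it is silent on Aim 7.

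Several places bear on why monitoring might be short. The eligibility table for peripartum women says that "current wireless signals will only be available on the postpartum ward", and exclusion criterion 1 says "The ICU at MRRH is a closed unit in a separate building from the postpartum ward". Item 17 plans to interview roughly "15 women with less than 24 hours of monitoring". Item 21 logs outside causes, "e.g. electricity outages or cellular network disruptions, and stock outs".

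**The concern.** Hours of monitoring are not a baseline characteristic. They arise after enrolment, and some of what shortens them may also shape recovery and cost. Transmission works only on the postpartum ward, and the ICU is elsewhere. A woman moved off the ward for good before 12 hours would therefore miss the gate and never be asked about expenditure.

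At stake is what the expenditure rates describe. As Aim 7 is worded, a reader would take them to apply to the women enrolled after emergency cesarean. In fact they would apply to those who reached 12 hours of monitoring. The comparison of expenditure by functional status could be affected too, if the missing women differ on both. Answers not collected at 6 and 12 weeks cannot be recovered by later analysis.

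**Working it through.** The plan gives no figure on this point, so there is none to reproduce. The check has four steps.

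**1. Which Aim 7 analyses need the device?**

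| Analysis | Data used | Needs motion data? |
|---|---|---|
| Early mobility summary | device | yes |
| Return to function by early mobility | device and survey | yes |
| Expenditure by early mobility | device and survey | yes |
| Function at each time point | survey | no |
| Impoverishing and catastrophic expenditure rates | survey | no |
| Expenditure by functional status | survey | no |

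The gate has a rationale for the first three rows. It restricts the last three without one.

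**2. Can monitoring time relate to outcome?** It can. Only direct ICU admission after delivery is excluded at entry. A later transfer is not mentioned, but the ward-only signal means that it would interrupt monitoring. Unrelated causes are also possible: outages, stock-outs, discomfort, or a woman's choice to stop. The documents do not say how these divide.

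**3. How large could the bias be?** Every input here is an assumption, because the documents give none of them.
- *f*: share of enrolled women under 12 hours, 5% to 30%.
- *RR*: risk of the outcome in those women relative to the rest, 0.5 to 3.
- *p*: rate among surveyed women, 20% for illustration.

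True rate = *p* × [(1 − *f*) + *f* × *RR*].

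Relative error of the surveyed rate = 1 / [(1 − *f*) + *f* × *RR*] − 1.

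| *f* | *RR* | True rate | Surveyed 20% is, in relative terms |
|---|---|---|---|
| 5% | 2 | 20% × 1.05 = 21.0% | 4.8% too low |
| 10% | 2 | 20% × 1.10 = 22.0% | 9.1% too low |
| 20% | 2 | 20% × 1.20 = 24.0% | 16.7% too low |
| 30% | 3 | 20% × 1.60 = 32.0% | 37.5% too low |
| any | 1 | 20.0% | unbiased |
| 10% | 0.5 | 20% × 0.95 = 19.0% | 5.3% too high |
| 30% | 0.5 | 20% × 0.85 = 17.0% | 17.6% too high |

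**4. What if the early leavers are a mixture?** Let a share *s* have deteriorated, with *RR* = 3, and let the rest have relative risk *r*. The bias is zero when 3*s* + (1 − *s*)*r* = 1, that is, *s* = (1 − *r*) / (3 − *r*).
- *r* = 1: *s* = 0, so any deteriorated share makes the rate too low.
- *r* = 0.8: *s* = 0.2 / 2.2 = 9%.
- *r* = 0.5: *s* = 0.5 / 2.5 = 20%.

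Above these shares the surveyed rate is too low; below them it is too high.

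**The case against.** The best defence is that Aim 7 is one chain, from early motion to recovery to financial risk. Expenditure is explicitly compared by early mobility, so a minimum monitoring time defines the women with a usable exposure. This stands for the motion analyses, and it rules out saying that expenditure has no link to motion. It does not cover the plain rates or the comparison by functional status.

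A reader might infer that the rule keeps only women with an uneventful first half day, and that expenditure must therefore come out too low. The documents do not support that. Item 22 asks for 12 hours of monitoring, without requiring the first 12, consecutive hours or freedom from complications. Women treated on the ward stay eligible, as do those who deteriorate later. The device stores up to 6 hours of data (item 8), so a brief absence need not end monitoring. Transfer for deterioration is an inference from the ward-only signal and the separate ICU, and non-clinical causes are named.

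A reader might also extend the point to depression and complications. Those data are collected under the same gate, but Aim 7 plans no rate for either.

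Finally, much of the repair material exists already. Item 20 records start and stop times and interruptions, item 11 reviews charts for severe outcomes, and the SAP summarises monitoring length under Reach. The number and severe-outcome profile of the women excluded can be derived. Their expenditure cannot.

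**Conclusion.** The point holds as an avoidable selection. A rule suited to the motion analyses is applied to survey results that do not need it, and it depends on a post-enrolment event that may relate to clinical course. Underestimation of the expenditure rates is plausible if early deterioration ends monitoring. Neither direction nor size can be fixed from the documents: the bias is nil if women under 12 hours carry equal risk and reversed if they carry less. Over the assumed ranges, the surveyed rate runs from 37.5% too low to 17.6% too high in relative terms, and those figures illustrate sensitivity only.

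The reach is limited to Aim 7. The Aim 1 analysis uses severe maternal outcomes up to hospital discharge in all eligible women and is untouched. This is a worthwhile, inexpensive improvement and no threat to the main result.

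**What to change.** Amend items 22 and 23 so that every enrolled woman discharged alive, and who has not withdrawn, is invited whatever her hours of monitoring. Apply the 12-hour rule only to analyses using the motion metric. In Aim 7, report the expenditure rates for all surveyed women and separately for under 12 hours and 12 hours or more, with the number of women monitored for a short time and the reasons.

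The cost is a short amendment, a few more automated calls and some call-backs by research assistants. The calling system and the five-attempt rule are in place, and women who took part in monitoring already receive survey instruction at the item 16 interview. A woman never monitored would need that instruction at another contact. The motion association loses nothing. Controls have record review only, so the rates would still describe women enrolled in intervention blocks.

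If the gate is kept, label the expenditure rates as applying only to women with at least 12 hours of monitoring, and report the number, reasons and severe-maternal-outcome profile of those excluded.

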Most maternal deaths occur immediately around childbirth³ and approximately 45% in the first 24 hours.⁴ As such, the promotion of facility-based childbirth has been a corner stone of strategies to reduce maternal and neonatal deaths in low and middle-income countries.^{5,6} However, despite increases in the proportion of women delivering at facilities, reductions in mortality and morbidity have not been as rapid as expected.⁵ Evidence points to delays at the facility in the recognition of complications and timely intervention as once cause of morbidity and mortality.⁷⁻¹² Recognizing the critical timeframe in the immediate postpartum period, current guidelines from WHO call for close monitoring during this time.¹³ Similarly, nursing standards in resource-rich settings recommend physiologic monitoring every 15 minutes for the first 2 hours postpartum, then every fours for the first 24 hours.^{14 15} Sustaining such high frequency monitoring remains a challenge even in resource-rich settings.^{16 17} In RLS contexts such as Mbarara, Uganda, where staff-to-patient ratios may be as high as 1:50,¹⁸ such normative standards around monitoring are unattainable with current systems of physiologic monitoring.

Abnormalities in physiologic signs have been shown to predict subsequent in-hospital mortality and morbidity amongst emergency department and medical ward patients.¹⁹⁻²³ In response to these findings, health care systems in resource-rich settings have introduced “Track and Trigger” protocols and “Early Warning Scores” to identify abnormalities in physiologic signs and activate appropriate responses.²⁴ In the case of heart disease, combining early warning of potential illness with

appropriate medical response has reduced rates of cardiac arrest, readmissions to critical care, and mortality.²⁵⁻²⁷ Similar strategies have been recommended in an obstetric setting, where the most common causes of mortality are hemorrhage, hypertensive disease, and sepsis, accounting for 27.1%, 14.0% and 10.7% of maternal deaths worldwide.²⁸ These conditions are commonly associated with abnormal physiologic signs—hemorrhage causing tachycardia and hypotension; pre-eclampsia/eclampsia causing hypertension and hypoxia; and sepsis causing fever, tachycardia, hypotension, and hypoxia.^{29,30}

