7. To evaluate if motion in the early post-operative period is related to functionality, mobility and wellness during recovery from cesarean delivery and how recovery relates to financial risks after cesarean delivery.

Methodology

Setting: The research will be carried out in the Department of OB/GYN MRRH in Mbarara, Uganda. This facility is the primary referral hospital in southwest Uganda. It performs ~ 10,000 deliveries per year (~ 30/day), has a maternal mortality ratio of 460 per 100,000 live births (~50-60 deaths per year)

and a cesarean delivery rate of 40%. All women delivered by cesarean are followed and monitored by postgraduate doctors with assistance from midwives. In this facility, postgraduate doctors complete medical training including a two-year internship and practice independently for several years prior to postgraduate training in OB/GYN. Consultant/Specialist OB/GYN supervisors oversee clinical care from home or in-hospital depending on clinical acuity. There are currently 13 consultants/specialists, 39 postgraduate doctors in the institution, and 40 midwives with clinical privileges in the department. The physician to patient ratio ranges from 1:8 during the day to 1:25 during the night and weekends.

Study Population:

The following types of participants will be recruited for study purposes:

- 1) Clinicians: Consultants/Specialists and nurse/midwives with clinical duty on the maternity ward at MRRH during the study period.
- 2) Peripartum women delivered by emergency cesarean during the study period.

Study Intervention:

The intervention in this study is the use of a wireless monitor to perform physiologic monitoring of women undergoing emergency cesarean delivery for the first 24 hours after completion of the cesarean.

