Aim 1: The primary outcome measure is the rate of severe maternal outcome (SMO). This is a composite measure drawn from WHO near miss morbidity criteria (Table 2). Secondary outcome measures include: the maternal mortality rate, maternal near miss rate and case fatality rates for postpartum hemorrhage, hypertensive disease and sepsis – the three most common causes of maternal death. The event rates for both primary and secondary outcomes will be compared using logistic regression models with the Generalized Estimating Equations approach to take into account of patients within clustering (due to time blocks). Exploratory analyses will be used to determine if a) the intervention is more powerful in certain subgroups of women and b) if any provider was consistently different in maternal outcomes regardless of intervention. The interaction between study arm and comorbidities (HIV, hypertension, pulmonary, cardiac or kidney disease, malaria) or provider will be tested in the logistic regression models. Subgroup effects will be reported if there is strong evidence of heterogeneity of intervention effect

Aim 2: We will apply the RE-AIM model to conduct a quantitative evaluation of the implementation of the intervention used in Aim. Table 4 describes the primary metrics to be measured and data sources from which it will be collected.

RE-AIM Implementation Science Framework ^{37,38}			
Metric	Dimension	Study Measure	Data source
Reach	Proportion of target population that participated in the intervention	
 Percent of women with successful placement of biosensor after delivery Total length of time for monitoring over 24hrs postpartum Percent of women participating in monitoring for 24 hrs 	
 Physiologic data from biosensor Time of delivery from chart records & theatre log books
Efficacy	Success rate if implemented as in guidelines	
 Percent of women with HR, BP, RR and Tp available at least every 4 hours for 24 hrs after delivery Percent of appropriate SMS alerts sent 	
 Physiologic data from biosensor RA review of mobile phones for SMS alerts and time of receipt

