On average approximately 8-10 emergency cesarean deliveries are performed at MRRH daily. Thus, in a two week block we estimate ~ 112 emergency cesareans performed. We plan to capture all women delivered by emergency cesarean during an intervention block thus minimizing the risk of selection bias based on the severity level. Assuming 85% of women consent to participation (conservative estimate based on >90% recruitment in prior studies)^{5,74,75}, this yields an estimated 95 women per block. Over 12 months of enrollment, we will therefore have 13 intervention blocks and 13 control blocks. This yields an estimated 1,235 women in the intervention group and 1,235 in the control group. Assuming an intraclass correlation coefficient of 0.01, the effective sample size after taking account of clustering is 633 per group. This will allow us to detect a difference of 5.7% in the SMO rate between the two study arms, with a two-sided significance level of 0.05, and 80% power, assuming a baseline rate of SMO of 13% ^{71,73}

Risk/Discomforts and protections

Clinicians:

- Risk of false alerts, alert fatigue: Clinicians will be asked to hold a mobile phone and respond to alerts. It is possible that alerts of physiologic sign abnormalities may not correspond to a developing or established clinical abnormality and in responding to the alert clinicians may become fatigued from alerts. Study investigators will monitor for this occurrence and the impact on clinician performance and duties and adjust study protocols as necessary
- Risk of diversion and interruptions to work on other patients: Alerts sent to clinicians may also prompt them to perform additional exams or clinical procedures that may or may not be beneficial to the patients from which alerts were received. This may divert attention or human resource away from other clinical needs. We will monitor for any diversions resulting in substandard clinical care. If these occur we will consider protocol modifications. Any safety concerns or adverse events arising because of false alerts or diversions will be communicated to the IRB within 10 days.

Peripartum women:

- Theoretical risk of exposure to radio emissions from Wi-Fi from the biosensor: There is a theoretical risk of exposure to Wi-Fi signals from the biosensor worn by women participating in

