##### Secondary outcomes

- Maternal Mortality ratio: Number of maternal deaths per 100,000 livebirths

**Commented [BAA1]:** Consider livebirths for only women included in the trial? Or consider livebirths for all women at the hospital

NCT ID: 2019P000885

Document Date: September 26th 2021

- Case fatality rate for
  - Hemorrhage – deaths/total number of hemorrhage cases
  - Hypertensive disorders of pregnancy- deaths/total number of HDP cases
  - Sepsis - deaths/total number of sepsis cases

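### Logistic GEE is not usable for the three cause-specific case fatality rates: with plausibly about one death per arm, an arm without deaths is likely, and the model then gives no finite odds ratio and can print a spurious p-value

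*Protocol*

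**What the plan says.** The protocol's Aim 1 analysis lists maternal mortality, near miss, and "case fatality rates for postpartum hemorrhage, hypertensive disease and sepsis" as secondary outcomes. It applies one method to all of them: "The event rates for both primary and secondary outcomes will be compared using logistic regression models with the Generalized Estimating Equations approach", with the two-week blocks as clusters. The sample size section gives "13 intervention blocks and 13 control blocks" and adds: "This yields an estimated 1,235 women in the intervention group and 1,235 in the control group".

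The SAP (Secondary outcomes) keeps the three rates with cases as the denominator, for example "deaths/total number of hemorrhage cases". Its Aim 1 analysis says that secondary event rates will be computed for both kinds of period, but it ties its mixed-effects logistic comparison to the primary outcome. A margin comment there leaves the choice between a mixed model and GEE open.

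Neither document gives an expected number of deaths, a sparse-event method, or a statement that these outcomes are descriptive only. The mortality inputs are general ones. The hospital "has a maternal mortality ratio of 460 per 100,000 live births" (Setting), and the three conditions are described as "accounting for 27.1%, 14.0% and 10.7% of maternal deaths worldwide" (opening background).

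**The concern.** A logistic comparison of two arms needs deaths in both. If one arm has none, the log odds ratio has no finite maximum. What gets reported then depends on where the software stops iterating and which variance it uses.

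With only a handful of cause-specific deaths expected, the analysis as planned could end in three ways: no estimate, an estimate with a meaningless p-value, or a change of method made after the deaths have been seen. Maternal death is a result that readers will quote, and the SAP makes no multiplicity adjustment. A false signal of benefit or harm from one or two deaths is therefore a real risk.

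**Working it through.** **The plan's own figures.** Women per arm: 112 × 0.85 ≈ 95 per block, and 13 × 95 = 1,235. Effective size: 1,235 / (1 + 95 × 0.01) = 633, which the SAP uses as the number of women per arm. The plan states no figure for deaths, so the rest is built from its inputs.

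**Expected deaths (assumption).** 1,235 × 0.0046 = 5.68 per arm. Multiplied by 0.271, 0.140 and 0.107, this gives 1.54 hemorrhage, 0.80 hypertensive and 0.61 sepsis deaths.

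**Chance of an arm without deaths.** Treat deaths as Poisson with mean λ in each arm, arms equal: P = 1 − (1 − e^−λ)². For hemorrhage, e^−1.54 = 0.214 and 1 − 0.786² = 0.38. The number of cases does not enter.

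| Assumption | Deaths per arm (hemorrhage / hypertensive / sepsis) | Chance of at least one empty arm |
|---|---|---|
| 1,235 women, 460 per 100,000 | 1.54 / 0.80 / 0.61 | 38% / 70% / 79% |
| 1,235 women, 60 deaths per 10,000 (upper yearly count in Setting) | 2.01 / 1.04 / 0.79 | 25% / 58% / 70% |
| All eligible women, 13 × 112 = 1,456, at 460 | 1.82 / 0.94 / 0.72 | 30% / 63% / 74% |
| SAP's 633 per arm, at 460 | 0.79 / 0.41 / 0.31 | 70% / 89% / 93% |
| 1,235 women, mortality doubled | 3.08 / 1.59 / 1.22 | 9% / 37% / 51% |
| 1,235 women, mortality tripled | 4.62 / 2.39 / 1.82 | 2% / 18% / 30% |

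The 1,456 comes from "in a two week block we estimate ~ 112 emergency cesareans performed". The chance that at least one of the three models meets an empty arm is 1 − 0.617 × 0.301 × 0.207 = 96% in the first row, and 1 − 0.98 × 0.824 × 0.703 = 43% in the last.

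**What GEE prints with exactly one empty arm.** Assume 8 cases per block, so 104 per arm, with one death against none. Under working independence, each arm contributes Σ(block residual)² / (Σp(1−p))² to the sandwich variance.

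- Arm with one death: p = 1/104. One block has residual 1 − 8/104 = 0.923 and twelve have −0.077. The sum of squares is 0.923, divided by 0.990², which gives 0.941.
- Empty arm: as the fitted risk μ tends to 0, every block residual is −8μ. The contribution is 13 × 64μ² / (104μ)² = 1/13 = 0.077, however small μ is.

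The standard error is √(0.941 + 0.077) = 1.01, while the log odds ratio runs off without limit. In statsmodels the fit stopped at −21.9 with SE 1.01 and p of about 10^−104, from a single death.

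Null simulations used 26 blocks, independence GEE with sandwich SE, 500 runs per setting, and an assumed 30 or 100 cases per arm. Every fit with exactly one empty arm gave p<0.05. The chance of that pattern is 2e^−λ(1 − e^−λ) = 34%, 50% and 50% for the three causes (35–51% in the simulations), so false positives would be far above the nominal 5%.

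**When both arms have deaths.** A Wald test needs |ln(b/a)| / √(1/a + 1/b) ≥ 1.96. For 1 v 8, this is 2.079 / 1.061 = 1.96. The next smallest splits are 2 v 10 and 3 v 11. Summing Poisson probabilities, rejection given a finite estimate is at most 0.02% at 460 per 100,000. It is at most 3.3% with mortality tripled and intervention deaths halved. The simulated GEE rejected in none of the finite fits at the hospital ratio.

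**All-cause mortality.** With 5.68 deaths per arm, the chance of an empty arm is 0.7%, or 6% if intervention deaths are halved. The same Wald calculation gives about 6% power for a halving.

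**The case against.** **The SAP may already settle this.** It only computes secondary rates and models the primary outcome, so case fatality could be read as descriptive. That has some force, but the SAP does not say it and does not withdraw the protocol's comparison. Moving to the SAP's mixed logistic model would not help, because an empty arm leaves that odds ratio infinite too.

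**The death counts are not the trial's own.** This stands. The ratio is hospital-wide and the cause shares are worldwide. The protocol chose women with emergency cesarean because they are at higher risk (inclusion criterion 2 for peripartum women). A reader might infer that the documents imply 0.6 to 1.5 cause-specific deaths per arm. They do not; that is one assumption within a range of about 0.3 to 4.6. At triple mortality, an empty arm is no longer a frequent event for hemorrhage (2%), though it remains 18% and 30% for the other two.

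**Not every mortality outcome fails.** A reader might extend the point to overall mortality. At 1,235 per arm that model is nearly always estimable; its weakness is power.

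**The harm is not only missed effects.** A reader might conclude that these models simply cannot reject. That describes only trials with deaths in both arms, where rejection is very rare rather than impossible. In the other common case the error runs the opposite way, towards false significance. How it shows depends on software: another program may stop with a warning or use a different variance.

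**These are secondary outcomes.** True. The plan claims power only for the primary composite, which this point does not touch.

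**Conclusion.** The concern holds for the three case fatality rates. At the hospital-wide ratio, an arm without deaths has a chance of 38%, 70% and 79%, and the planned model then has no finite odds ratio and can report a false p<0.05. With deaths in both arms it practically never rejects. The size depends on assumed mortality, equal arms, Poisson deaths and, for the simulated p-values, assumed case numbers and a sandwich variance with working independence. At triple mortality the chances fall to 2%, 18% and 30%. For all-cause mortality the finding is limited to very low power, about 6% for a halving. The protocol and SAP also need to agree on whether these outcomes are compared at all.

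**What to change.** Reconcile the protocol's Aim 1 analysis with the SAP's, before outcome data are compared by arm:

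- Remove logistic GEE for the three case fatality rates. Report deaths over cases by arm, keeping the SAP's case denominator, with exact 95% CIs and no p-value.
- If a comparison is wanted, name a penalised (Firth) or exact method in advance.
- Report all-cause deaths over eligible women by arm with a CI. State that the trial is not powered for mortality and that a non-significant result will not be read as no effect.

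The cost is some SAP wording and a few lines of code. The trial gives up a modelled odds ratio for cause-specific fatality. The exact intervals ignore clustering by block, which so few deaths cannot estimate; the SAP should say so.
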